#### Table 14.1.4.3: Changes in methotrexate up to Week 12: tabulation

Tabulation per treatment group (and overall) of the change in MTX dose (decrease/no change/increase).

Population: safety.

#### Table 14.1.4.4: Use of methotrexate up to Week 12: Descriptive statistics of the average weekly dose

Descriptive statistics per treatment group (and overall) and per study period of the average weekly dose (mg/week).

Frequency tabulation per treatment group (and overall) of the average weekly dose, categorized as:

<10 ;  
 [10,15] ;  
 ]15,20] ;  
 >20 mg/week.

Population: safety.

### **7.9.3. Tables for the whole 24 weeks period**

Similar tables, using the 11 treatment arms of Chapter 3:

**Table 14.1.4.5: Changes in methotrexate over the whole study period: tabulation**

**Table 14.1.4.6: Use of methotrexate over the whole study period: Descriptive statistics of the average weekly dose**

### **7.9.4. Listings**

**Listing 16.2.5.4: Exposure to methotrexate: eCRF data**

Listing per treatment group and per subject of all data related to the use of methotrexate, as recorded in the eCRF.

Population: safety.

**Listing 16.2.5.5: Exposure to methotrexate: Derived data**

Listing per treatment group and per subject of all derived parameters related to the use of methotrexate.

Population: safety.

## **8. DEFINITIONS OF EFFICACY TABLES, LISTINGS AND FIGURES**

Mock tables, listings and figures are provided in a separate document.

All analyses will be run on the ITT population, unless specified otherwise.

General comment on the efficacy data listings: listings will present the observed-case time points, with imputed data (for components) clearly flagged. The LOCF- or NRI-imputed time points will not be shown.

General comments on the observed-case analysis:

- Is done for efficacy tables and listings, but not for efficacy plots.
- Is done for Baseline, Week 12 and Week 24 in the descriptive statistics.
- Is done for Week 12 only in the inferential statistics.
- Is done for ITT only; not for per-protocol.

## 8.1. ACR20, ACR50, ACR70 AND ACR-N

### 8.1.1. Parameters

ACR20 response when:

- $\geq 20\%$  improvement from baseline in SJC66, and
- $\geq 20\%$  improvement from baseline in TJC68, and
- $\geq 20\%$  improvement from baseline in at least 3 of the following 5 items:
  - Pain VAS (taken from the HAQ-DI)
  - Patient's Global Assessment of Disease Activity VAS
  - Physician's Global Assessment of Disease Activity VAS
  - Total HAQ-DI score
  - CRP.

Subjects who do not meet this criterion are non-responders.

If any of the 7 components of the ACR20 would be missing, then this missing component will be imputed using the value of the last preceding nonmissing visit. If all components are missing, then the derived ACR20 will remain missing. Imputation of such cases for the tables will be done there using LOCF or NRI like any other missing value.

Subjects who discontinue within the first week so that ACR20/50/70 responses cannot be determined will be classified as non-responders.

The ACR50 and ACR70 responses are derived using the same algorithm, but with 50% and 70% cutoffs respectively.

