#### **8.8.1.1 Datasets or Populations Analyzed**

All randomized subjects who received at least one dose of study medication and have at least one post-Baseline efficacy assessment will be included in the efficacy analysis (intent-to-treat [ITT]).

A secondary per-protocol analysis will be performed to confirm the ITT analysis, excluding subjects with major protocol deviations (such as Baseline CRP within normal range, Baseline TJC68 <8, Baseline SJC66 <6, <80% study medication compliance, or use of forbidden concomitant medications). Full details of the major protocol deviations will be described in the statistical analysis plan, with adherence to analysis sets agreed upon prior to database lock and unblinding.

All randomized subjects who received at least one dose of study medication will be included in the safety analysis.

All randomized subjects who received at least one dose of GLPG0634 and who have at least one PK measurement will be included in the PK analysis.

Reasons for study termination will be tabulated.

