Other applicable factors, if any, will also be included in the models. Quality of Life data (FACIT fatigue scale and SF-36 questionnaire) will be analyzed descriptively. Exploratory between-group comparisons will also be done at each post-Baseline time point using analysis of (co)variance models on the changes from Baseline with factors treatment, Baseline value, region and previous use of biologics.

Handling of discontinued subjects during the 24-week treatment period:

CONFIDENTIAL

- Subjects who discontinue within the first week so that ACR20/50/70 responses cannot be determined will be classified as nonresponders.
- For all discontinued subjects, their last observed nonmissing result will be used in the subsequent visits (last observation carried forward algorithm). Also for the ACR20/50/70 responses as part of the secondary/supportive analyses.

A descriptive sensitivity analysis by country, geographic region and previous use of biologics will be performed for the ACR criteria response rates.

Further exploratory analyses may be added when deemed useful to understand the data.

Graphical presentations may be added to facilitate the overall interpretation of the study results.

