#### 2.1.1. Efficacy data

Study period	Treatment groups	Analysis populations	Imputation method
“Chapter 2”: Periods 1+2 together (full 24 weeks period)	
The 7 original groups:
 
 
– Placebo
 
– GLPG0634 q.d. dosing groups:                             
 
• 50 mg q.d.
 
• 100 mg q.d.
 
• 200 mg q.d.
 
 
 
– GLPG0634 b.i.d. dosing groups:                             
 
• 25 mg b.i.d.
 
• 50 mg b.i.d.
 
• 100 mg b.i.d.
 
 
 
 
For the subjects in the placebo and low dose groups who switched to 100 mg/day during the second study period: they will be handled as if they discontinued at Week 12, and will be imputed from Week 12 onwards in the second study period.                      (Details: see further in the SAP)
	
ITT: all subjects randomized, exposed at least once, and with post-baseline data for at least one efficacy parameter.
 
Per-protocol: subpopulation of ITT, excluding all critical (=major) protocol deviations. This is decided during the blind review meeting before final database lock.
	
Observed case, non-responder imputation (NRI), last observation carried forward (LOCF): depending on the parameter; is specified later when all parameters are discussed.

Study period	Treatment groups	Analysis populations	Imputation method

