**Note that the primary endpoint of the study is the ACR20 at Week 12 in the ITT population, using NRI imputation.**

The ACR-N is derived using the following formula:

$$\text{ACR-N} = \text{MIN} [ \% \text{ improvement in TJC68, } \% \text{ improvement in SJC66, MED } \% \text{ improvement in (patient's global assessment, physician's global assessment, patient's assessment of pain, HAQ-DI, CRP) } ]$$

So this is taking the smallest of the percentage increases in SJC66, TJC68, and the third of the remaining 5 parameters. In case the ACR-N is negative (i.e., the subject actually worsens instead of improves), then the ACR-N is replaced by a 0. The ACR-N is therefore a number between 0 and 100.

The ACR-N represents the percentage NN% according to which the subjects would have been an "ACRNN" responder.

(See further sections on how to derive these components.)

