#### **Table 14.2.1.1.1: ACR20: Summary with overall p-value and pairwise comparisons versus placebo**

Logistic regression model at each time point, modeling the responders. Factors in the model are: treatment, region, and previous use of biologics.

Per time point, the table will present:

- Overall type-III p-value for all explanatory factors in the model.
- Per group: number and percentage of responders, difference in percentage responders versus the placebo group (GLPG0634 minus placebo), together with a 95% confidence interval of this difference (as provided by SAS PROC FREQ).
- Per group: p-value for pairwise comparison versus the placebo group, derived from contrasts within the overall regression model. These p-values will be presented both as uncorrected p-values as well as corrected for multiplicity according to Hommel's closed-testing method (SAS PROC MULTTEST).

The "raw" SAS PROC output must be provided in a statistical appendix listing.

The table will show:

- NRI in ITT and in per-protocol
- LOCF in ITT and in per-protocol
- observed-case in ITT (descriptive at Week 12 + 24; inferential statistics at Week 12 only).

Table to be created for the Week 12 interim analysis as well, cut off at Week 12. ITT only.

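### The primary ACR20 analysis with non-responder imputation leaves out dosed subjects who have no post-baseline efficacy value, and partial Week 12-window data can bypass the imputation for a withdrawn subject (minor)

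*SAP*

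**What the plan says.** **Who counts as a non-responder.** Protocol 8.8.1.3 (Methods of Analysis) says: "Subjects who discontinue within the first week so that ACR20/50/70 responses cannot be determined will be classified as nonresponders". SAP 6.1.2.3 repeats the rule, and so does SAP 8.1.1: "Subjects who discontinue within the first week so that ACR20/50/70 responses cannot be determined will be classified as non-responders".

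**Who is analysed.** SAP 8.1.1: "Note that the primary endpoint of the study is the ACR20 at Week 12 in the ITT population, using NRI imputation". SAP 2.1.1 defines ITT as "all subjects randomized, exposed at least once, and with post-baseline data for at least one efficacy parameter". Protocol 8.8.1.1 sets the same restriction: "All randomized subjects who received at least one dose of study medication and have at least one post-Baseline efficacy assessment". For Table 14.2.1.1.1 the SAP lists "NRI in ITT and in per-protocol", LOCF in the same two sets, and observed-case in ITT. It adds: "Table to be created for the Week 12 interim analysis as well, cut off at Week 12. ITT only".

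**How a Week 12 response is built.**
- SAP 3.3 places early discontinuation visits and unscheduled visits in windows by study day. Week 12 is Days 71 to 98.
- SAP 3.4 selects within a window separately for each parameter.
- SAP 8.1.1 fills any missing ACR component from the most recent earlier visit that has it. "If all components are missing, then the derived ACR20 will remain missing", and only then does NRI or LOCF apply.
- SAP 4.4.3 defines NRI as acting on a missing response.
- SAP 6.1.2.3 says that, for discontinued subjects, visits later than discontinuation are imputed.

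**The concern.** The plan presents the primary rate as one in which dropouts count as failures. Two features depart from that.

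**1. Denominator.** A dosed subject who leaves with no post-baseline efficacy value is the clearest case for the first-week rule. That subject is outside ITT, so neither the rule nor NRI reaches them. First-week dropouts who do have a value stay in ITT and would be Week 12 non-responders under NRI anyway. Removing failures raises an arm's rate, and unequal removal shifts the difference from placebo.

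**2. Partial data in the Week 12 window.** NRI acts only when ACR20 is missing, and ACR20 is missing only when all seven components are. One component in Days 71-98 is therefore enough for a withdrawn subject to be scored mainly on earlier values. The result could then depend on an incidental measurement.

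This is the primary endpoint, and the interim based on it supports phase III dose selection (protocol 8.8.1.5, SAP 6.2). A shift of a few points in one arm could matter when six active arms are ranked.

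**Working it through.** **Plan's own figure.** Inputs from protocol 8.8.2: 85 per arm, alpha 0.05/6 = 0.00833, chi-square test. A two-sided pooled chi-square without continuity correction gives power of 89.8% (48% vs 20%), 91.2% (70% vs 40%), 80.9% (45% vs 20%) and 78.4% (66% vs 40%). The stated values are 90%, 90%, 80% and 80%. They reproduce within 2 points and do not depend on this issue.

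**Part 1: size of the denominator effect.** The documents give no count of affected subjects, so k = 1, 3 or 5 of 85 per arm is an assumption. With rate p when the k subjects count as non-responders, excluding them gives p × 85/(85 - k). For example, 41/85 = 48.2% becomes 41/80 = 51.3%. Change in the difference from placebo, in points, for k = 1 / 3 / 5:

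| Rates | Both arms | Active arm only | Placebo only |
|---|---|---|---|
| 48% vs 20% | +0.33 / +1.02 / +1.75 | +0.57 / +1.76 / +3.00 | -0.24 / -0.73 / -1.25 |
| 70% vs 40% | +0.36 / +1.10 / +1.88 | +0.83 / +2.56 / +4.38 | -0.48 / -1.46 / -2.50 |

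Unadjusted pooled chi-square p with nobody excluded, and with 5 excluded from placebo only (the least favourable case for the active arm):

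| Responders of 85 | None excluded | 5 excluded, placebo only |
|---|---|---|
| 41 vs 17 | 0.00010 | 0.00029 |
| 38 vs 17 | 0.00058 | 0.0014 |
| 60 vs 34 | 0.00006 | 0.00027 |
| 56 vs 34 | 0.00072 | 0.0026 |

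Excluding 5 from both arms or from the active arm only gives smaller p values than excluding nobody. All values are below 0.00833, so they pass Bonferroni and hence Hommel. The planned test is a logistic regression with region and previous biologics; the chi-square follows the sample-size section and is an approximation to it.

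Power also differs little. If 48% and 20% apply to subjects with data and both arms lose 1 to 5, power is 89.4% to 87.5% when they are excluded and 89.2% to 86.2% when they count as non-responders.

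**Part 2: applying the SAP 8.1.1 rule.** Assumed subject, withdrawn after a full Week 8 visit:

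| Component | Baseline | Week 8 | Days 71-98 |
|---|---|---|---|
| SJC66 | 12 | 8 | none |
| TJC68 | 20 | 14 | none |
| Each of three VAS | 60 | 40 | none |
| HAQ-DI | 1.5 | 1.2 | none |
| CRP | 15 | 10 | 14 |

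Not all components are missing, so six are carried from Week 8. Improvements are 33% (SJC66), 30% (TJC68), 33% on each VAS, 20% on HAQ-DI and 7% on CRP. Both joint counts and four of the five other items pass, so the subject is a Week 12 responder. Without the CRP result, all seven are missing and NRI makes the same subject a non-responder. Each subject rescored in this way moves an arm by 1/85 = 1.2 points; three move it by 3.5.

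**Does another output isolate these cases?** For Part 1, disposition Tables 14.1.1.2 and 14.1.1.7 and Listing 16.2.3.2 show the excluded subjects, but no planned version of the primary table includes them. For Part 2, the general comment in SAP 8 places component-imputed data inside the observed-case time points. The observed-case table therefore does not separate them; only the listing flags do.

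**The case against.** **Part 1.**
- The post-baseline requirement is prespecified consistently in both documents, and modified ITT sets are common. That is so, but the plan also gives a contrary rule for the same subjects and does not reconcile the two.
- The first-week rule is not empty: a first-week dropout whose only post-baseline value comes from the unwindowed follow-up visit stays in ITT. This stands.
- The excluded group is narrow. CRP is an efficacy parameter and part of the chemistry panel, so one post-dose sample brings a subject into ITT. This stands and limits the likely size.
- The all-dosed rate can be recovered as responders divided by dosed N, barring as-treated reassignment. This holds for the rate, but not for the model-based, Hommel-corrected p value.
- Replacing the primary set after the sponsor has viewed unblinded Week 12 summaries is debatable. I agree, so the fix adds a result and replaces nothing.

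**Part 2.**
- SAP 6.1.2.3 already sends visits after discontinuation to imputation. This largely answers the case of later safety samples, but the SAP does not say that it overrides the component rule. It also does not clearly cover a partial early discontinuation visit that falls in the window.
- A reader might infer that the creatinine retests in protocol 8.3.4 are a documented route. They are only a possible one: the documents do not say that a retest measures CRP, and a retest could coincide with the follow-up visit, which is not windowed.
- A blanket rule that partial data mean non-response would override a response already met on observed components. This is correct, and the fix avoids it.

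**Conclusion.** Both points hold on the text, and both are minor.

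1. Dosed subjects with no post-baseline efficacy value leave the primary denominator, although the plan's own rule would count them as non-responders. Under the assumed 1 to 5 per arm, the difference changes by about -2.5 to +4.4 points. The upper end needs five such subjects in the active arm and none on placebo.
2. A withdrawn subject with some, but not all, components in Days 71-98 can be scored a responder through carry-forward in the NRI analysis. How often this would happen is unknown.

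A reader might infer more than this. The documents do not support any of the following:
- that the primary conclusion or the stated power fails: the power reproduces, and the placebo comparisons at planned effects keep their result in every 5-subject exclusion scenario;
- that NRI is generally undone by carry-forward: dropouts with nothing in the window are non-responders;
- that the excluded subjects are hidden: disposition tables and a listing show them;
- that carrying forward a lost component for a subject who attends Week 12 is a fault: it is ordinary item imputation.

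**What to change.** (i) Add to Table 14.2.1.1.1 an ACR20 Week 12 NRI analysis in all randomized and dosed subjects, counting those without post-baseline efficacy data as non-responders, as SAP 8.1.1 already intends. Keep the prespecified ITT result beside it for consistency with the interim. Log the addition in SAP 6.3.2.

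(ii) In SAP 8.1.1, state for the NRI analysis that:
- samples taken after discontinuation do not create a Week 12 ACR20 value;
- for a subject who withdrew before the Week 12 assessment, ACR20 is taken from the components observed in Days 71-98. The subject is a responder only if the criterion is met on those components and otherwise a non-responder, with no carry-forward from earlier visits.

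Component carry-forward for subjects who attend Week 12, and complete early discontinuation visits in the window, stay as they are now.

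Cost: a few sentences, one extra table and possibly slightly lower response rates.

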**Note that the primary endpoint of the study is the ACR20 at Week 12 in the ITT population, using NRI imputation.**

The ACR-N is derived using the following formula:

$$\text{ACR-N} = \text{MIN} [ \% \text{ improvement in TJC68, } \% \text{ improvement in SJC66, MED } \% \text{ improvement in (patient's global assessment, physician's global assessment, patient's assessment of pain, HAQ-DI, CRP) } ]$$

So this is taking the smallest of the percentage increases in SJC66, TJC68, and the third of the remaining 5 parameters. In case the ACR-N is negative (i.e., the subject actually worsens instead of improves), then the ACR-N is replaced by a 0. The ACR-N is therefore a number between 0 and 100.

The ACR-N represents the percentage NN% according to which the subjects would have been an "ACRNN" responder.

(See further sections on how to derive these components.)

#### The time to ACR20 response

= (date of first time ACR20 response is reached) – (date of first medication intake) + 1 day, if the subject achieved ACR20 response during the initial 12 weeks treatment period, or  
= MIN (date of the Week 12 visit , date of trial termination) – (date of first medication intake) + 1 day, in case the subject did not achieve ACR20 response at any time during the initial 12 weeks treatment period.

Next to this, the visit during which the ACR20 response was first recorded will be analyzed as well:

- Week 1
- Week 2
- Week 4
- Week 8
- Week 12
- Never (i.e., subject did not achieve ACR20 response during the initial 12 weeks of treatment).

The time to ACR50 response and the time to ACR70 response are defined in the same way.

Note that the study period 2 cannot be used for the time-to-event derivation, because of the predefined potential treatment shifts at Week 12.

Note that if for a specific visit both the regular CRP as well as the high-sensitive CRP are available, the high-sensitive CRP will be used for the derivation of the percentage change from baseline and also for the ACR20/50/70/N.

Note that the percentage change from baseline remains missing if the baseline value itself equals zero.

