#### **8.6.2.5 Week 12 (Visit 7)**

The Week 12 visit (Visit 7) will take place on Day 85 ± 2 calendar days relative to the start of study medication intake.

- Any remaining study medication as well as empty study medication containers will be returned to the investigator and an accountability check will be performed.
- Any AEs that have occurred since signing the ICF will be documented, and any changes in concomitant medication will be reported.
- Vital signs will be measured.
- A 12-lead ECG will be performed.
- A physical examination will be performed.
- The subject diary card will be collected, a summary will be recorded in the eCRF, and a new subject diary card will be dispensed.
- Blood samples for measurement of PK and PD parameters will be collected.
- Serum CRP will be measured.
- SJC66 and TJC68 evaluations will be performed.
- Physician's and Patient's Global Assessments of Disease Activity will be completed.
- The subject will complete the HAQ-DI.
- The subject will complete the FACIT fatigue scale and the SF-36 questionnaire.
- Hematology, clinical chemistry, and urinalysis (dipstick and microscopy) tests will be performed on samples collected at this visit. A urine pregnancy test will be performed on females of childbearing potential.

CONFIDENTIAL

At visit 7, subjects on placebo who have not achieved a 20% improvement in SJC66 and TJC68 will be re-randomized (automatically via IXRS) to treatment to receive GLPG0634 100 mg q.d. or 50 mg b.i.d. doses in a blinded fashion, subjects on 50 mg q.d. who have not achieved a 20% improvement in SJC66 and TJC68 will be assigned to 100 mg q.d. and subjects on 25 mg b.i.d. who have not achieved a 20% improvement in SJC66 and TJC68 will be assigned to 50 mg b.i.d. All will continue the study until Week 24. Subjects in the other groups will maintain their randomized treatment until Week 24.

When all of these procedures have been performed, the study medication will be dispensed according to the information provided using IXRS and the date of the next visit confirmed.

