**Table 14.2.1.1.15: Time to ACR20 response: Summary with overall p-value and pairwise comparisons versus placebo**

Descriptive statistics per treatment group.

Between-group comparison (overall and all pairwise comparisons versus placebo)

P-values are generated from a Cox proportional hazards regression model. Factors in the model are: treatment, region, and previous use of biologics.

The table will present:

- Per group: N (number of events, number of censored, number in total), mean (SE), median, quartiles.

- Overall type-III p-values for treatment, region and previous use of biologics.
- Per group: p-value for pairwise comparison versus the placebo group. These p-values will be corrected for multiplicity according to Hommel's closed-testing method as implemented in SAS PROC MULTTEST. The uncorrected p-values will also be presented.

A frequency table of the time-to-event in categories (Week 1, Week 2, Week 4, Week 8, Week 12, never) will also be presented.

The "raw" SAS PROC output must be provided in a statistical appendix listing.

Population: ITT.

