**Figure 14.2.1.1.6: Time to ACR20 response: Kaplan-Meier plot**

Ascending Kaplan-Meier plot per treatment group.

Population: ITT.

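### Censoring Week 12 non-responders on their own visit day lifts the Week 12 end of the Kaplan-Meier time-to-response curves above the true cumulative ACR20/50/70 response

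*SAP*

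**What the plan says.** SAP 8.1.1 sets the event time from actual dates: "date of first time ACR20 response is reached) – (date of first medication intake) + 1 day". A subject who does not respond in the first 12 weeks is censored at "MIN (date of the Week 12 visit , date of trial termination", also counted in days from first intake. Nothing later is used, because "study period 2 cannot be used for the time-to-event derivation". The rule extends to the other two endpoints: "The time to ACR50 response and the time to ACR70 response are defined in the same way".

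Protocol 8.6.2.5 allows a spread of visit days: the Week 12 visit "will take place on Day 85 ± 2 calendar days". SAP 3.3 labels any visit from Day 71 to Day 98 as Week 12, so the real spread may be wider.

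The outputs concerned are Figures 14.2.1.1.6 to 14.2.1.1.8, each specified as "Ascending Kaplan-Meier plot per treatment group", and Table 14.2.1.1.15 with its ACR50 and ACR70 repeats. These tables print, per arm, the number of events, "number of censored, number in total), mean (SE), median, quartiles". They also give a frequency count of the visit of first response, with a *never* category.

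The SAP has no rule that moves Week 12 to a common day, places censoring after the last Week 12 assessment, or uses a discrete-time or interval-censored method.

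**The concern.** Response can be seen only at a visit. A subject seen on Day 83 without a response has completed the Week 12 assessment, and the SAP's own frequency table counts that subject as *never*. The Kaplan-Meier estimator treats the same subject as lost on Day 83 and lets him or her go on to respond at the rate seen in those examined on Days 84 to 87. Here a known outcome is handled as missing follow-up. The risk set shrinks through the visit window, so each later Week 12 response makes a larger step.

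At stake are the right-hand end of three published-style curves per endpoint family and any median or quartile first reached there. One table could show a finite median time to response alongside a *never* count above half.

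**Working it through.** The plan states no figure for this analysis, so there is none to reproduce. The only planning number needed is 85 subjects per arm (Protocol 8.8.2). Two further inputs are assumptions because the documents do not give them: the share of an arm first responding at Week 12, and how visit days spread inside Day 83 to Day 87.

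**Formula.** Let S0 be the share without response before Week 12, p the fraction of those first responding at Week 12, w_d the share of Week 12 visits on day d, and R_d the share not yet seen at the start of day d. With events before censorings on ties and no dropout:

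KM at the end = 1 − S0 × Π over d of (1 − p × w_d / R_d)

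The true cumulative response is 1 − S0 × (1 − p).

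**Worked example.** Of 100 subjects, 35 respond before Week 12. The other 65 are seen 13 per day on Days 83 to 87, with 2 first responses each day. In truth 35 + 10 = 45 of 100 responded.

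| Day | At risk | Factor | Cumulative response |
|---|---|---|---|
| 83 | 65 | 1 − 2/65 = 0.9692 | 37.0% |
| 84 | 52 | 1 − 2/52 = 0.9615 | 39.4% |
| 85 | 39 | 1 − 2/39 = 0.9487 | 42.5% |
| 86 | 26 | 1 − 2/26 = 0.9231 | 47.0% |
| 87 | 13 | 1 − 2/13 = 0.8462 | 55.1% |

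The curve ends at 55.1% against a true 45%, and a median of Day 87 is printed although fewer than half responded. With 30% before and 10% at Week 12, the same calculation gives 50.3% against 40%.

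**Range.** Excess of the Kaplan-Meier end value over the true value, in points, from the formula. The range in each cell reflects different shares responding before Week 12.

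| First responding at Week 12 (assumed) | Even over Days 83–87 | Triangular over Days 83–87 | Even over Days 84–86 | All on Day 85 |
|---|---|---|---|---|
| 3% | 3.4 to 3.7 | 4.1 to 4.4 | 2.3 to 2.4 | 0 |
| 5% | 4.7 to 5.9 | 5.5 to 7.0 | 3.2 to 3.9 | 0 |
| 8% | 8.4 to 9.0 | 9.9 to 10.6 | 5.6 to 6.0 | 0 |
| 10% | 8.6 to 10.6 | 10.1 to 12.5 | 5.9 to 7.1 | 0 |

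Simulation with 85 per arm and no dropout, at ever-response rates of 34%, 43%, 56% and 70%, gave mean excesses of 3.4 to 4.3, 5.1 to 6.8, 7.4 to 10.3 and 8.6 to 12.4 points for the four rows. Its three visit spreads were even, triangular, and 85% of visits on Day 85 with the rest within ±2 days. A narrower window reduces the bias. Clustering on Day 85 with a few stragglers does not reliably do so, because very few subjects remain at risk on the last days.

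A low-rate arm of ACR70 type (2% before, 3% at Week 12) gains about 4 to 5 points. The excess in any one arm varies widely: for 35% plus 10% with even visits, the 5th to 95th percentiles were 2.7 to 19.9 points.

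**False medians.** Among simulated arms in which fewer than half responded, a median was printed in roughly 45% to 70% with 35% before and 10% at Week 12, and in roughly 20% to 30% with 35% and 5%.

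**Cox model.** For 35% + 10% against 60% + 10%, the mean hazard ratio was 1.99 with actual days and 2.00 with nominal days. With equal arms, rejection at the 5% level was 4.7%.

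**The case against.** The strongest reply is that little rests on these outputs. The primary analysis is Week 12 ACR20 with non-responder imputation and logistic regression, and uses no event times. Time to response is a planned method in Protocol 8.8.1.3 and SAP 6.1.2.3, but it is not among the synopsis secondary endpoints or the objectives. The SAP marks its interim outputs explicitly, and these tables and figures carry no such mark, so they are not planned input to the interim dose selection. The Cox comparison barely moves, and the frequency count in the same table shows the correct cumulative response. All of this stands and limits the importance of the point. The count reveals the contradiction, but it does not correct the curve or the median.

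Three stronger readings are tempting and are not supported:

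- A reader might infer a fixed overstatement of 8 to 12 points for ACR20, ACR50 and ACR70 alike. That range needs about 8% to 10% of an arm to respond first at Week 12, a share the documents do not give. At 3% to 5% the excess is smaller.
- A reader might infer that medians and quartiles are wrong in every arm. Censoring at the Week 12 visit cannot act before those visits. Any quantile reached by Week 8 is the same under either rule. A quantile affected at Week 12 becomes too early or falsely finite.
- A reader might infer that the comparison with placebo is compromised. The hazard ratios above show otherwise, provided visit-day spread is similar across arms.

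**Conclusion.** The rule is wrong as written for the Kaplan-Meier curves and the quantiles read from them. The bias is upward whenever Week 12 visits fall on more than one day and some subjects first respond there. With visits spread within ±2 days, the mean excess is about 3 to 4 points if 3% of an arm first responds at Week 12, 5 to 7 at 5%, 7 to 11 at 8% and 9 to 12 at 10%. These figures assume no dropout before Week 12 and visit timing unrelated to response. The excess is smaller with a narrower spread and zero if all visits share one day. A median or quartile reachable only at Week 12 can be reported although too few subjects responded. This is a correction to secondary descriptive output. It gives no reason to doubt the primary result or the Cox comparison.

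**What to change.** In SAP 8.1.1, derive time to ACR20, ACR50 and ACR70 response on nominal visit days (8, 15, 29, 57, 85) for both events and Week 12 censoring, with events ordered before censorings on ties. Alternatively, censor subjects assessed at Week 12 without a response at one common day after the last Week 12 assessment, for example Day 98, the upper bound of the Week 12 window in SAP 3.3. Both give the same end value. The nominal-day version is cleaner, since Day 98 nominally credits a subject seen on Days 83 to 87 with 11 to 15 unobserved days (98 − 87 and 98 − 83). Keep the actual termination date for subjects who leave before Week 12.

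With either change, the worked example returns 45.0% and no median. Without dropout, the curve ends at the crude cumulative response. With 8% dropout among subjects not yet responding, an excess of about 0.8 to 1.5 points remains, which is ordinary dropout censoring.

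The cost is one sentence in the SAP, a small change to the derivation program and an entry in the SAP's record of changes. No new data are needed, and no planned interim output has to be reissued.
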